- 3 Subjects with an eGFR of >45 and <60 mL/min/1.73 m² based on the Week -1 (baseline) serum creatinine sample will undergo blood sampling for post-contrast serum creatinine measurement 48-96 hours after imaging during the procedure and any subsequent procedure where imaging contrast is used.
- 4 eGFR will be calculated using the Chronic Kidney Disease Epidemiology Collaboration (CKD-EPI) equation. For all subjects, if the calculated eGFR is reduced >25% from baseline (Week -1), the investigator should repeat the serum creatinine test as soon as possible, but no later than 1 week after the first test. If the repeated calculated eGFR remains >25% from baseline, the investigator should refer the subject for further renal functions evaluations, including review by a nephrologist. Similarly, if a subject's eGFR drops to ≤45 mL/min/1.73 m², then he/she will have renal function monitored and managed by a nephrologist as an additional safety measure following this event and until the event is resolved. In either case, the decrease in eGFR will be reported as an AE.
- 5 Only calculated for those subjects who have serum creatinine measured at this time point.
- 6 Performed per the hospital's standard of care and analyzed at site.
- 7 Compliance testing in relation to antihypertensive medications.

Table 4 Schedule of Blood and Urine Sample Collection (Crossover Phase)

[figure not shown]
Period		Re-Screening Period	Treatment	Follow-Up Period		
Visit Time Point		Up to Wk -4	D 0	D 2 to D 4 (48-96 h) ¹	Wk 4	Mth 6
Visit Window					+/-7 D	+/-4 Wk
Serum chemistry	Sodium	X			X	X
	Potassium	X			X	X
	Serum chloride	X			X	X
	BUN/urea	X			X	X
	Uric acid	X			X	X
	Cystatin C	X			X	X
	Glucose	X			X	X
	Serum creatinine	X		X ²	X	X
	eGFR ³	X		X ⁴	X	X
Liver panel	AST (SGOT)	X			X	X
	ALT (SGPT)	X			X	X
	Alk phos	X			X	X
	Bilirubin (conj)	X			X	X
	Bilirubin (total)	X			X	X
	LDH	X			X	X
	Albumin	X			X	X
	Total protein	X			X	X
Hematology	RBC	X			X	X
	WBC (total and differential)	X			X	X
	HGB	X			X	X
	HCT	X			X	X
	Platelets	X			X	X

Period		Re-Screening Period	Treatment	Follow-Up Period		
Visit Time Point		Up to Wk -4	D 0	D 2 to D 4 (48-96 h) ¹	Wk 4	Mth 6
Visit Window					+/-7 D	+/-4 Wk
Coagulation	aPTT	X				
	PT	X				
	INR	X				
	ACT ⁵		X			
Urinalysis	Specific gravity	X			X	X
	pH	X			X	X
	Glucose	X			X	X
	Ketones	X			X	X
	Protein (total)	X			X	X
	Bilirubin	X			X	X
	Hemoglobin	X			X	X
	Nitrite	X			X	X
	WBC	X			X	X
	RBC	X			X	X
	Bacteria	X			X	X
	Crystals	X			X	X
	Casts	X			X	X
	Spot microalbumin	X			X	X
	Spot creatinine	X			X	X
Other	Pregnancy test (serum)	X			X	X

Abbreviations: ACT = activated clotting time; Alk phos = alkaline phosphatase; ALT (SGPT) = alanine aminotransferase (serum glutamate pyruvate transaminase); aPTT = activated partial thromboplastin time; AST (SGOT) = aspartate aminotransferase (serum glutamic oxaloacetic transaminase); BUN = blood urea nitrogen; D = day; eGFR = estimated glomerular filtration rate; h = hour; HCT = hematocrit; HGB = hemoglobin; INR = international normalized ratio; LDH = lactate dehydrogenase; Mth = month; PT = prothrombin time; RBC = red blood cell(s); Scrn = screening; WBC = white blood cell(s); Wk = week; Yr = year

[figure not shown]
- 1 For applicable subjects only (see footnote 2).
- 2 Blood sampling for post-contrast serum creatinine measurement is dependent on when imaging procedure is performed and the subject's eGFR measurement: blood is to be drawn and measured 48-96 hours after any procedure where imaging contrast is used and ONLY on subjects with an eGFR of >45 and <60 mL/min/1.73 m² (as measured at the study re-screening visit).
- 3 eGFR will be calculated using the Chronic Kidney Disease Epidemiology Collaboration (CKD-EPI) equation. For all subjects, if the calculated eGFR is reduced >25% from baseline (as measured at re-screening visit), the investigator should repeat the serum creatinine test as soon as possible, but no later than 1 week after the first test. If the repeated calculated eGFR remains >25% from baseline, the investigator should refer the subject for further renal functions evaluations, including review by a nephrologist. Similarly, if a subject's eGFR drops to ≤ 45 mL/min/1.73 m², then he/she will have renal function monitored and managed by a nephrologist as an additional safety measure following this event and until the event is resolved. In either case, the decrease in eGFR will be reported as an AE.
- 4 Only calculated for those subjects who have serum creatinine measured at this time point.
- 5 Performed per the hospital's standard of care and analyzed at site.

Figure 1 Overall Study Design

[figure not shown]
The subject, sponsor, hypertensionist/nephrologist, and research team performing the screening and follow-up assessments will be blinded to the subject's randomized treatment assignment (Treatment Arm or Sham Control Arm). The interventionalist and catheterization laboratory (cath lab) staff will be unblinded.

- 2 At a screening visit, after written informed consent has been provided, initial screening assessments will be made. Subjects will then attend for magnetic resonance angiography (MRA) to assess renal vasculature before the start of the run-in period. For sites that would prefer to use computed tomography angiography (CTA) instead, agreement may be reached with the sponsor on a case-by-case basis (depending upon local regulatory approvals and site capacity). Subjects must have an estimated glomerular filtration rate (eGFR) of >45 mL/min/1.73 m² confirmed before imaging at screening. Subjects who are currently taking antihypertensive medications will down-titrate their medications, if necessary, so that they are taking 0 antihypertensive medications at the start of the run-in period.
- 3 Subjects will take 0 antihypertensive medications from the start of the run-in period (Week -4). During the run-in period, a safety visit will take place approximately 2 weeks before the procedure (Week -2). Further study assessments and a final check of eligibility criteria will be performed approximately 1 week before the procedure (Week -1), including office blood pressure and ambulatory blood pressure monitoring (ABPM) measurements.
- 4 Subjects may be admitted on Day -1 for logistical reasons. For the day of the procedure (Day 0), flexibility in scheduling is permitted (up to 1 week), e.g. due to cath lab availability, based on physician discretion and with careful consideration of subject safety. Randomization 1:1 (Treatment Arm : Sham Control Arm) will be performed in the cath lab/special procedure lab on the day of the procedure (Day 0), after the subject has been sedated and undergone diagnostic renal angiography.
- 5 Subjects will continue to use 0 antihypertensive medications during the first 8 weeks after the procedure (except for emergencies). After 8 weeks, antihypertensive medications are permitted, if necessary (see Appendix I).
- 6 Study unblinding will be performed after the last subject has completed the 1-year follow-up visit.
- 7 Crossover from the Sham Control Arm to the Treatment Arm may be allowed, at the discretion of the treating investigator, after the Data Safety Monitoring Board (DSMB) has reviewed the 1-year data from all subjects and the study has been unblinded.

Figure 2 Study Flow Diagram: Subject Screening, Run-in, and Treatment

BP = blood pressure; DBP = diastolic blood pressure; N = number of subjects; SBP = systolic blood pressure

Figure 3 Study Flow Diagram: Post-Treatment Milestones and Endpoints

AE = adverse event; BP = blood pressure; DBP = diastolic blood pressure; DSMB = Data Safety Monitoring Board; eGFR = estimated glomerular filtration rate; N = number of subjects; SBP = systolic blood pressure.

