Subjects will be enrolled in the study at the time they sign the informed consent form. No study-specific procedures will be performed until after the subject has provided written informed consent.

Subject Inclusion Criteria

Subjects must meet all of the following inclusion criteria to be eligible and undergo the procedure:

Prior to run-in period

1. Subject has provided written informed consent.
2. Male or female subject, aged ≥ 18 and ≤ 80 years at time of enrollment.
3. If subject has a documented history of uncontrolled hypertension (see definition in Definition of Terms section of protocol) and is currently taking no (0) antihypertensive medications, he/she must:
 - Have 3 office blood pressure measurements with a mean office systolic blood pressure (SBP) of ≥ 140 mmHg and ≤ 180 mmHg AND mean office diastolic blood pressure (DBP) ≥ 90 mmHg, and
 - Be willing to adhere to the no-medication regimen for at least 12 weeks (4-week run-in period and 8-week post-treatment period).
4. If subject has a documented history of uncontrolled hypertension (see definition in Definition of Terms section of protocol) and is currently taking 1 or 2 antihypertensive medications, he/she must:
 - Have 3 office blood pressure measurements with a mean office SBP of ≥ 120 mmHg and ≤ 180 mmHg and
 - Be willing to discontinue his/her antihypertensive medication(s), and to adhere to the no-medication regimen for at least 12 weeks (4-week run-in period and 8-week post-treatment period).
5. Investigator judges that the subject can be discontinued safely from all current antihypertensive medication (where applicable) and managed safely for at least 12 weeks (4-week run-in period and 8-week post-treatment period) without antihypertensive medication intake.
6. Female subjects of childbearing potential must agree to use acceptable methods of contraception (as defined in the protocol), from the time of informed consent through to the last follow-up visit.
7. Subject agrees to have all study procedures performed and is able and willing to comply with all study follow-up visits and protocol requirements.

End of run-in period

8. Subject has 3 office blood pressure measurements with a mean office SBP of ≥ 140 mmHg and ≤ 180 mmHg AND mean office DBP ≥ 90 mmHg.
9. Subject has a mean 24-hour ambulatory SBP of ≥ 135 mmHg and ≤ 170 mmHg with $\geq 70\%$ valid readings (as determined by ABPM measurement device).

Exclusion Criteria

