- 1 The run-in period starts approximately 4 weeks prior to the planned date of the procedure. The subject must start the run-in period on 0 antihypertensive medications. In the case of subjects taking 1 or 2 antihypertensive medications that require down-titration, these subjects must down-titrate their medications prior to the start of the run-in period. If a subject takes antihypertensive medication during the run-in period but still wishes to enter the study, one re-start of the run-in period is possible if this is acceptable to the physician as well as the subject, and if the physician believes that the subject will be compliant.
- 2 Where possible, subjects who discontinue early from the study will undergo these procedures.
- 3 Subjects may be admitted on Day -1 for logistical reasons. For the day of the procedure (Day 0), flexibility in scheduling is permitted (up to 1 week), e.g. due to cath lab availability, based on physician discretion and with careful consideration of subject safety.
- 4 For applicable subjects only (see footnote 12).
- 5 One set of 3 measurements using the same cuff and same arm as used at screening. See office blood pressure manual.
- 6 ABPM measurements must be collected at the same time as office BP measurements, where applicable. Office BP measurements are collected before ABPM set-up.
- 7 24-Hour ABPM at this time point is only performed if office BP measurements meet the inclusion criteria.
- 8 At 1 year only.
- 9 An MRA will be performed for assessment of renal vasculature. For sites that would prefer to use CTA instead, agreement may be reached with the sponsor on a case-by-case basis (depending upon local regulatory approvals and site capacity).
- 10 Scheduled at the initial screening visit, then performed and assessed prior to the start of the run-in period to check renal artery anatomy. If either of the imaging tests has been performed within 12 months prior to the time of enrolment, review of the images by the core lab may be performed, with consultation by the sponsor and principal investigator, to determine if a repeat of the protocol imaging test is needed to assess anatomical eligibility. Must be performed after screening serum creatinine sampling and only to be performed if eGFR based on this sample is $>45 \text{ mL/min/1.73 m}^2$.

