- 11 If the renal duplex ultrasound assessment at 6 months cannot be performed, or if the results are non-diagnostic, CTA/MRA/renal angiography may be performed if agreed with the sponsor (depending upon local regulatory approvals and site capacity). If renal artery stenosis of >60% or any other significant abnormality is suspected or confirmed by renal duplex ultrasound, as evaluated by the core laboratory, or as the result of other clinical assessments, those findings should be confirmed using the imaging modality used at screening (CTA/MRA/renal angiography). The choice of imaging may be changed at the discretion of the investigator and should be discussed with the sponsor.
- 12 Subjects with an eGFR of >45 and <60 mL/min/1.73 m² based on the screening serum creatinine sample will undergo blood sampling for post-contrast serum creatinine measurement 48-96 hours after imaging at screening. Subjects with an eGFR of >45 and <60 mL/min/1.73 m² based on the Week -1 (baseline) serum creatinine sample will undergo blood sampling for post-contrast serum creatinine measurement 48-96 hours after imaging during the procedure and any subsequent procedure where imaging contrast is used.
- 13 See Table 3 for details of blood and urine parameters. Tests to be done in the case of ET will be as for the Month 6 visit, but excluding compliance tests.
- 14 For measurement of serum creatinine only (all subjects). This sample must be taken prior to imaging at screening, because the eGFR value based on this measurement will be used to assess whether the subject is excluded or may proceed to have the screening imaging assessment.
- 15 Activated coagulation time (ACT) only is performed on Day 0, per the hospital's standard of care.
- 16 For compliance testing only.
- 17 No antihypertensive medications are permitted from the start of the run-in period until the subject has completed the visit at 8 weeks post-treatment (except in the case of emergencies).
- 18 Antihypertensive medications may be given after the 8-week visit if necessary (according to pre-defined criteria and proposed titration schedule).

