5.2. General Considerations

5.2.1. General Methods

Two unblinded team members (either two statisticians or a statistician and a statistical programmer) will be assigned for all analyses. This will allow for discussion of output and direct QC of statistical programming on the exact same dataset.

In general, continuous variables will be summarized with descriptive statistics (n, mean, SD, range, median, and interquartile range). The difference between groups will be presented and the normal approximation will be used to calculate two-sided 95% confidence intervals (CIs). Change from baseline, when relevant, will be computed as the paired mean difference and 95% CI of the mean difference at each time point.

For all continuous primary and secondary blood pressure endpoints, changes over time will be additionally explored in mixed effects repeated measures analyses, including the values at all time points.

Categorical variables will be summarized as frequencies and percentages. Relative risks and 95% CIs will be computed.

All statistical analyses will be performed using SAS® Version 9.4 or higher (SAS Institute, Cary, NC 27513, USA).

For each variable, the baseline value will be defined as the last value collected before the procedure.

There will be no formal hypothesis testing conducted in the study. Ninety-five percent CIs, when presented, are intended to be descriptive in nature only. For binary variables, CIs will be calculated via exact binomial methods. For continuous variables, the CI of the mean will be constructed using the normal approximation.

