5.2.2. Adjustments for Covariates

Analysis of changes in blood pressure measures will be adjusted for baseline values using analysis of covariance (ANCOVA). Raw mean values will be presented, however, comparisons between groups will include the baseline value of the associated measure as described below. There is no other planned adjustment for covariates.

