5.6. Blood Pressure

Blood pressure will be summarized at each visit for the various blood pressure measures: office BP (Screening (Week -8), run-in (Week -2), baseline (Week -1), 4 weeks, 8 weeks, 3 months, 6 months, 1 year and 2 years), 24-hour ABPM (baseline [Week -1], 8 weeks, 6 months and 1 year), daytime ABPM (baseline [Week -1], 8 weeks, 6 months and 1 year) and nighttime ABPM (baseline [Week -1], 8 weeks, 6 months and 1 year). Both systolic and diastolic blood pressure will be presented separately. The mean values at each visit will be presented along with the mean change from baseline (and the matched baseline data for each visit).

The number and percentage of subjects with any decrease from baseline in the various blood pressure measures will be presented. The number and percentage of subjects with any, \geq 5 mmHg, \geq 10 mmHg, and \geq 20 mmHg decreases in blood pressure at each time point will be presented.

Ninety-five percent CIs for the change in mean blood pressure will be computed as well as the 95% CI for the percentage of subjects with any decrease in blood pressure.

These analyses will be conducted in the ITT analysis set.

In order to assess the totality of the data over time, changes in blood pressure at the 8-week, 3-month, 6-month, and 1-year and 2-year (office BP only) visits will be plotted over time by treatment group and assessed via a mixed effects repeated measures model. All available data at the time of analysis will be included in the model. This analysis will be conducted in the ITT analysis set with available data.

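### The Week -2 office blood pressure, taken off drug before randomisation, is left out of the office SBP and DBP comparisons and could make the 8-week estimate more precise

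*Protocol*

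**What the plan says.** **Protocol.** Table 1 schedules office blood pressure at screening, Week -2 and Week -1. Its footnote on the office row sets one method for all of them: "One set of 3 measurements using the same cuff and same arm as used at screening". Week -2 and Week -1 both fall in the no-drug period: "No antihypertensive medications are permitted from the start of the run-in period until the subject has completed the visit at 8 weeks post-treatment", emergencies excepted. Randomisation follows on Day 0. The Week -1 reading is the one tested against inclusion criterion 8 ("Subject has 3 office blood pressure measurements with a mean office SBP of ≥ 140 mmHg and ≤ 180 mmHg", together with mean office DBP of at least 90 mmHg). No entry range is stated for Week -2.

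**SAP.** Section 5.2.1 states: "For each variable, the baseline value will be defined as the last value collected before the procedure". Section 5.2.8 adds that, if there are several valid baseline readings, the one nearest the procedure is used. Section 5.2.2 adjusts blood pressure comparisons by ANCOVA for the baseline of the same measure and then says: "There is no other planned adjustment for covariates". Section 5.6 summarises office blood pressure at "run-in (Week -2), baseline (Week -1), 4 weeks, 8 weeks, 3 months, 6 months, 1 year and 2 years", so Week -2 is reported, but the repeated-measures model there names post-procedure visits only. Week -2 therefore enters no between-group comparison. Office SBP and DBP are secondary endpoints (SAP 3.4.2).

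**The concern.** A single-visit office blood pressure is a noisy guide to a subject's usual level. A second reading by the same method, a week or so earlier and also off drug, carries further information about that level. Because it precedes randomisation, adding it as a covariate cannot bias the treatment estimate. It can only change the standard error.

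The trial aims to judge, on about 80 evaluable subjects, whether the effect justifies a pivotal study. A narrower interval on office blood pressure would help that judgement, even though the SAP calls its intervals descriptive. What is at stake is precision on a secondary endpoint, using data already collected.

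**Working it through.** **1. The plan's own figure.** The documents state power only for 24-hour SBP: 80% for 5.1 mmHg with SD 8, two-sided alpha 0.05 and 80 evaluable subjects. With 40 per arm, the exact t calculation gives 80.4% and the normal approximation 81.4%, so the figure reproduces. No SD, power or precision is given for office blood pressure. The correlations below are therefore assumptions, shown as ranges.

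**2. Formula.** Let r1 be the correlation of Week -1 with Week 8, r2 that of Week -2 with Week 8, and r12 that between the two run-in readings. The residual variance with both covariates, relative to Week -1 alone, is

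1 − (r2 − r1·r12)² / [(1 − r12²)(1 − r1²)].

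If all three equal rho, this becomes (1 + 2·rho)/(1 + rho)². The second covariate costs a factor of about (80 − 4)/(80 − 5) = 76/75.

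**3. Equal correlations.**

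| rho | gross ratio | net ratio | equivalent N (80 / net ratio) |
|---|---|---|---|
| 0.3 | 1.6/1.69 = 0.947 | 0.959 | 83 |
| 0.5 | 2.0/2.25 = 0.889 | 0.901 | 89 |
| 0.6 | 2.2/2.56 = 0.859 | 0.871 | 92 |
| 0.7 | 2.4/2.89 = 0.830 | 0.842 | 95 |
| 0.8 | 2.6/3.24 = 0.802 | 0.813 | 98 |

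The variance falls by about 4% to 19%. Intervals narrow by about 2% (√0.959 = 0.979) to 10% (√0.813 = 0.902).

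**4. Run-in readings closer to each other than to Week 8.** This is plausible, since they are about a week apart and Week 8 is some 9 to 10 weeks away.

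| r1 | r2 | r12 | gross ratio | net ratio |
|---|---|---|---|---|
| 0.6 | 0.6 | 0.8 | 0.938 | 0.950 |
| 0.5 | 0.5 | 0.7 | 0.941 | 0.954 |
| 0.6 | 0.55 | 0.75 | 0.964 | 0.977 |
| 0.5 | 0.45 | 0.7 | 0.974 | 0.987 |
| 0.5 | 0.35 | 0.7 | 1.000 | 1.013 |

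For the second row: (0.5 − 0.35)² / (0.51 × 0.75) = 0.0225/0.3825 = 0.059, so the gross ratio is 0.941. The gain runs from about 5% to nothing. The last row is a loss of 1.3%, the price of the extra covariate.

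**5. Simulation with the entry limits applied.** There were 4,000 trials of 80 subjects, selected on Week -1 office SBP 140–180, office DBP at least 90 and ambulatory SBP 135–170. The assumed unselected office SBP had mean 152 and SD 14.

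| assumed correlations | SE, Week -1 only | SE, both | variance ratio |
|---|---|---|---|
| all 0.3 | 3.01 | 2.97 | 0.97 |
| all 0.5 | 2.68 | 2.55 | 0.91 |
| all 0.7 | 2.19 | 2.01 | 0.85 |
| r12 0.7, Week 8 0.5 | 2.69 | 2.64 | 0.97 |

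These agree with steps 3 and 4.

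**6. Role of the entry limits.** Under joint normality, selecting on Week -1 changes neither the residual variance given Week -1 nor that given both readings, so the ratio in step 2 is the same with or without the cut-off. With all three limits applied, the large-sample ratio at rho 0.5 was 0.900, against 0.889 without selection, so the limits do not enlarge the gain.

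**7. Visits after 8 weeks.** Assume r12 = 0.61 and a correlation of 0.3 between either run-in reading and a later visit. The gross gain is (0.3 − 0.183)² / (0.628 × 0.91) = 2.4%, and the net ratio is 0.976 × 76/75 = 0.989, a gain of 1.1%. At a later-visit correlation of 0.2 the net gain is about zero.

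**The case against.** The strongest reply is that nothing here is wrong. ANCOVA on one prespecified baseline is valid and unbiased, office blood pressure is secondary, and the SAP says its intervals are descriptive. SAP Section 7 shows that the single-baseline model was adopted following FDA guidance for a companion study and for consistency between the two studies. All of that stands, and it makes this an efficiency point. It does not show harm from one more pre-randomisation covariate.

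A second reply is that Week -2 may predict poorly. It falls only about two weeks into the no-drug period, and Table 3 shows blood and urine compliance tests at Week -1 but none at Week -2, so off-drug status there rests on the protocol rule and the subject diary. This also stands. It is why the range of gain has to start at zero.

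Three stronger readings are tempting, and the documents do not support them:

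- A reader might infer that the criterion 8 cut-off causes the loss or biases the comparison. Truncation does weaken the one covariate used: in the simulation the correlation of Week -1 with Week 8 falls from 0.50 to 0.35, while Week -2 keeps 0.40. But step 6 shows that it does not create the gain from adding Week -2, and randomisation after selection keeps ANCOVA unbiased.
- A reader might infer a gain at every visit. After 8 weeks, drugs may be titrated to an office SBP target, which should loosen the link to run-in values.
- A reader might translate the gain into office blood pressure power. The plan claims no such power and gives no SD from which to compute it.

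**Conclusion.** The point holds as a modest, low-cost gain in precision for office SBP and DBP at 8 weeks. The planned analysis is valid as it stands. The primary 24-hour SBP has only one pre-procedure ambulatory recording, so its analysis and stated power are unaffected.

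The size cannot be fixed from the documents. For 8-week office SBP, the variance falls by about 4% to 19% under equal visit correlations of 0.3 to 0.8, and by about 0% to 5% if the run-in readings are closer to each other than to Week 8. Later visits should gain little. The second pattern is at least as plausible as the first, so the upper figures should not be quoted alone.

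**What to change.** In SAP 5.2.2 and 5.6, state that for office SBP and DBP the 8-week ANCOVA and the office repeated-measures model include both the Week -1 and the Week -2 value of the same measure as covariates. Keep change from baseline defined against Week -1. With Week -1 in the model, the treatment estimate is the same whether the outcome is the change or the 8-week value.

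If Week -2 is missing, fill the covariate by a rule that ignores treatment arm, for example with the subject's Week -1 value. Say that this is covariate handling and not the endpoint imputation that SAP 5.2.3 excludes for secondary endpoints.

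SAP 5.2.4 allows aggregate results by arm to leave the DSMB after the 8-week interim. The sponsor should check whether that has happened. If it has, the two-covariate model should be labelled supportive, beside the planned one.

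Adjusting for the mean of the two readings did about as well in simulation (variance ratio 0.89 at rho 0.5 and 0.84 at rho 0.7). That used the 8-week value as outcome, so two separate covariates fit the plan's change score better.

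The cost is one degree of freedom, a few sentences in the SAP, and an office model that differs slightly from the ambulatory model and possibly from the companion study. No new data are needed.
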